3.4 Per Protocol Set

3.4.1 Per Protocol Set, Part 1

Per Protocol Set (PPS), Part 1 will consist of all subjects in the Efficacy Analysis Set, Part 1 without any important protocol deviations leading to exclusion from the PPS during the Part-1 period of the study. The PPS, Part 1 will be used as supportive analyses of primary and secondary endpoints for Part 1 only.

Protocol deviations are defined as any change, divergence, or departure from the study design or procedures defined in the study protocol. Important protocol deviations are a subset of protocol deviations that may significantly impact the correctness, accuracy, and / or reliability of the

study data or significantly affect a subject's rights, safety, or well-being. Section 3.4.2 details the deviations.

3.5 Safety Analysis Set

3.5.1 Safety Analysis Set, Part 1

All subjects treated with at least one dose of study medication in Part 1 of the study will be included in the Safety Analysis Set, Part 1. This population will be used for all the Safety analyses for Part 1.

3.5.2 Safety Analysis Set, Part 2

All subjects treated with at least one dose of study medication in Part 2 of the study will be included in the Safety Analysis Set, Part 2. This population will be used for all the Safety analyses for Part 2.

3.7 Pharmacokinetics Analysis Set, Part 1

The PK Analysis Set, Part 1 will include all subjects who received at least one dose of study medication in Part 1 of the study and had at least one blood sample taken at a later time to measure K0706 concentration level. This population will be used for PK-related analyses for Part 1.

3.8 All Enrolled Set, Part 2

[figure not shown]
All subjects who had a Part 2 visit, including the Part 2 baseline visit (e.g., eCRF Visit 13), will be included in the All Enrolled Set, Part 2. This population will be used for the summary of disposition, demographics and baseline characteristics for Part 2.

4. DATA HANDLING

4.1 Time Points and Visit Windows

4.1.1 General Definitions

All assessment days will be related to the first day of the first dose of study drug administration.

The date of the first dose of study drug administration for each subject will be taken from the 'Study Drug' or 'Date Drug Admin Form' eCRF forms at the Baseline Visit. If the date in these eCRF forms is missing, alternatively, the date of randomization will be used.

For all Part 2 subjects, the date of the first dose of study drug administration in Part 2 will be taken from the 'Study Drug form-2' eCRF form at Visit 13/11 (Baseline visit for Part 2, Week 40). If the date in this eCRF form is missing, alternatively, the date of the Visit 13/11 (Baseline visit for Part 2, Week 40) will be used.

The date of the last dose of study drug administration for each subject will be taken from the "Last Study Drug Details" eCRF form. If the date on this eCRF form is missing, alternatively, the date of the last dose from the "DOSING" eCRF form will be used for the imputation.

4.1.2 Definition of Baseline Value for Part 1 and Part 2

For all subjects, the Baseline period for Part 1 is defined as the period from informed consent to the first dose of study drug administration. For some variables, data from more than one assessment within the Baseline Period are collected prior to the first dose of study drug administration.

Unless otherwise specified, the baseline value for a variable for Part 1 is defined as the value of the last non-missing assessment or observation collected before the first dose of study drug administration for Part 1.

Assessments carried out on the day of the first dose of study drug administration, i.e., Day 1, are considered to have taken place before the first dose of study drug administration if the corresponding times have not been recorded.

Unless otherwise specified, for all Part 2 subjects, the baseline value for a variable for Part 2 is defined as the non-missing value collected at Visit 11 (i.e., the Week 40 visit of Part 1). Note that the baseline visit for Part 2 is labeled as Visit 13, and the baseline value is simply taken from Visit 11, per the study schedule. Also, per the study schedule, the start (i.e., first dose) of the study drug for Part 2 is scheduled to be administered on the same day of the visit date of Visit 11. However, in some cases, the start of the study drug administration for Part 2 actually took place after the visit date of Visit 11. That is, the study drug start date in Part 2 can be greater than the visit date of Visit 11. In such cases, the non-missing assessment or observation immediately prior to the start of the study drug administration for Part 2 will be taken as the baseline value for Part 2.

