3.2 Part 2 (Week 40 to Week 80)

3.2.1 Primary Objective

To assess the long-term safety/tolerability of K0706 in subjects with early PD

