9.3 Study Drug Exposure and Compliance

Study drug exposure will be evaluated using the	formulation dosing
separately and as pooled per visit total number of doses	administered for Part 1 and
Part 2. All exposures will be sum	marized using nominal units (mg) as wel
as equivalence-adjusted units in periods for each study p	part and overall for the entire treatment

period. The number and percent of doses administered per subject and the number of subjects with doses administered at each scheduled visit will be summarized using descriptive statistics by treatment arm (Part 1 and Part 2 separately) and in total for the Safety Population.

Cumulative observed exposure will sum per visit for nominal and equivalence-adjusted dosing separately at each visit, study part, and overall by formulation and as pooled across both formulations as applicable.

For Part 1, the percentage of doses administered per subject will also be summarized descriptively, defined as the total number of doses received per visit and overall in Part 1 divided by the total planned dose per visit and overall in Part 1, expressed as a percentage. Part 2 will be handled similarly, and the total overall in the pooled periods will also be described similarly.

Relative dosing intensity will be calculated as the cumulative observed exposure per visit, study part and overall divided by the expected per visit, study part, and overall exposure, respectively. The result will be expressed in units of percentage.

Incomplete dosing and its impact on exposure and compliance metrics will be evaluated as a potential protocol deviation prior to unblinding for any planned analysis. If confirmed, relevant exposure and compliance metrics will be adjusted accordingly.

All study drug administration data will be listed by subject.

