9.8 Safety Analyses

The analysis of safety parameters will be based on the Safety Population. In general, missing safety data will be analyzed without imputation or substitution. Treatment-emergent events will be described for Part 1 separately and for Parts 1 and 2 overall. Events will be considered

treatment-emergent if first appearing or worsening following initiation of study therapy and within 4 weeks after study therapy discontinues. See additional details in the SAP.

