2.1.2 Part 2 (Week 40 to Week 80)

Subjects who complete the EOT visit of Part 1 (Visit 11/Week 40) and who consent to participate in Part 2 of the study will be screened according to Part 2 eligibility criteria. Subjects randomized to placebo dosing in Part 1 will be rolled over to a high dose at Week 40 or their first dosing opportunity in Part 2. This will enable the collection of additional safety data for the high dose level. Subjects randomized to K0706 (either dose level) in Part 1 of the study will remain on the same dosing regimen in Part 2. All Part 2 subjects will continue taking the study drug (K0706) orally, once daily, for an additional 36 weeks. The Week 76 visit (Visit 19) is the EOT visit of Part 2. The Week 80 visit (Visit 20) is the follow-up visit of Part 2 to collect safety outcomes.

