9.0 SAFETY ANALYSES

All safety data will be summarized for Parts 1 and 2 of the study separately, using the Safety Analysis Set, Part 1 and Safety Analysis Set, Part 2, respectively.

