12.2 General rules for Statistical Reporting

In general, statistical reporting and analyses will be created separately for Part 1 and Part 2.

The default summary statistics for quantitative variables will be the number of observations (n), mean, SD, median, minimum (min) and maximum (max), for those subjects with data. In addition, geometric mean and CV% of geometric mean will be reported for PK parameters.

All summary statistics will be rounded (using the more decimal place than the raw value, except for the SD and SE values that will be presented to 2 more decimal places than the raw value, and minimum and maximum values that will be presented with the same decimal precision as the raw value. All summary statistics for PK data will be rounded (using the analysis) and presented to 3 significant figures, except for the geometric CV values that will be presented to 1 decimal place.

For qualitative variables, the number (n) and percentage (%) of subjects with non-missing data per category will be the default summary presentation, and where appropriate and present, the number of missing values as a "Missing" category. The number of subjects in the analysis population will be used as denominator for percentages calculation, unless stated otherwise in Tables, Figures and Listings (TFL) mock shell(s).

All statistical comparisons and tests will be performed at the significance level unless specifically stated otherwise.

All central laboratory test results will be provided in International System of Units (SI) and all local laboratory test results will be provided in conventional units.

For the TFL, the results will be summarized or presented in Refer to Appendix of the TLF mock shells for the SI unit corresponding to each laboratory test and the precision level in which each laboratory test is reported by the central laboratory.

Specifications for table, figures and data listing formats can be found in the TFL shells specifications for this study. Please refer to "2. General Format Guidelines" section within TFL shells for more details on presentation of results.

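### The SAP omits the Parts 1 and 2 combined safety summary that the protocol plans, so cumulative K0706 safety in the early-start arms is not tabulated

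*SAP*

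**What the plan says.** **Protocol.** Section 3.2.1 gives the primary objective of Part 2: "To assess the long-term safety/tolerability of K0706 in subjects with early PD". The synopsis makes TEAE incidence the Part 2 primary endpoint. Section 9.8 plans a combined view of events: "Treatment-emergent events will be described for Part 1 separately and for Parts 1 and 2 overall". Section 9.3 does the same for exposure after describing Part 1: "Part 2 will be handled similarly, and the total overall in the pooled periods will also be described similarly". Section 9.8.2, on laboratory data, vital signs and ECG, names no baseline and plans no combined-period change.

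**SAP.** Section 9.0 sets the rule: "All safety data will be summarized for Parts 1 and 2 of the study separately". Sections 9.1 (adverse events), 9.2 (laboratory), 9.3 (vital signs and weight) and 9.8 (exposure) repeat it. Section 12.2 makes it the default: "In general, statistical reporting and analyses will be created separately for Part 1 and Part 2". Section 3.5 defines a Part 1 safety set and a Part 2 safety set, and no set that spans both.

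For change from baseline in Part 2, SAP 4.1.2 states that "for all Part 2 subjects, the baseline value for a variable for Part 2 is defined as the non-missing value collected at Visit 11". If the first Part 2 dose comes later than that visit, the last value before that dose is used. SAP 2.1.2 keeps both K0706 arms on their existing regimen and moves former placebo subjects to K0706 at the start of Part 2.

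**The concern.** Long-term safety on K0706 concerns what happens from the first K0706 dose onward. For the two early-start arms, the SAP divides that period at Week 40 and never joins the pieces.

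- **Events.** Part 2 TEAE tables for these arms cover only subjects who completed Part 1, because Protocol 4.3.1 requires completion for entry. Anyone who stopped in the first 40 weeks, including for intolerance, is absent from the Part 2 denominator. Neither part's table gives incidence over the whole time on drug.
- **Changes.** Part 2 laboratory, vital-sign and weight changes start from a value taken after 40 weeks on K0706. For former placebo subjects the same column heading means change since starting K0706. SAP 9.2 and 9.3 also ask for an 'overall' column across the groups.

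At stake is whether the report contains a direct summary for the Part 2 primary objective, and whether a combined summary promised in the protocol is lost without comment.

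**Working it through.** The plan gives no figure to reproduce here, so the check is mainly a comparison of texts.

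**Step 1. The two documents side by side.**

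| Item | Protocol | Visible SAP text |
|---|---|---|
| Treatment-emergent events | Part 1, plus both parts together (9.8) | Part 1 and Part 2 separately (9.0, 9.1) |
| Exposure | Each part, plus pooled periods (9.3) | Each part separately (9.8) |
| Safety population | One population (9.5) | One set per part (3.5) |
| Laboratory, vital-sign and weight change over both parts | Not promised (9.8.2) | Not specified (9.2, 9.3) |
| ECG | No baseline stated (9.8.2) | Part 1 only (9.4) |

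The first two rows conflict. The fourth is a gap in both documents. The ECG row shows that the Part 2 baseline rule has no bearing on QTcF.

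**Step 2. What the Week 40 value is in each group.** In the low-dose and high-dose early-start arms it is an on-drug value. In former placebo subjects it is a pre-K0706 value, so their Part 2 change is already change since starting K0706.

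**Step 3. Share of exposure time.** Inputs: 40 weeks of treatment in Part 1 and end of treatment at Week 76 (SAP 2.1.1 and 2.1.2).

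- Part 2 treatment: 76 − 40 = 36 weeks.
- Share of an early-start subject's maximum K0706 time that falls after the Part 2 baseline: 36/76 = 0.474, or 47%.
- Share that falls before it: 40/76 = 0.526, or 53%.

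**Step 4. Number of subjects.** Inputs: 506 planned, randomized 1:1:1 (Protocol synopsis and 5.4.2).

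- Early-start: 2 × 506/3 = 337.3, about 337 before attrition.
- Former placebo: 506/3 = 168.7, about 169 before attrition.

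The documents do not give a roll-over rate. Assuming the same rate in every arm:

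| Assumed roll-over | Early-start in Part 2 | Former placebo in Part 2 |
|---|---|---|
| 60% | 202 | 101 |
| 80% | 270 | 135 |
| 100% | 337 | 169 |

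**Step 5. What 47% does and does not mean.** Suppose a measure drifts by a constant amount *d* per week on K0706. Early-start subjects show 36*d* in Part 2, and so do former placebo subjects. The 'overall' column then also shows 36*d* and distorts nothing. The untabulated quantity is the 76*d* of cumulative change in the early-start arms.

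Suppose instead that an effect *E* develops fully within the first 36 weeks on drug and then holds. Early-start subjects show about 0 in Part 2 and former placebo subjects show *E*. With equal roll-over, the 'overall' column shows (2/3) × 0 + (1/3) × *E* = *E*/3. The column's meaning therefore depends on the shape of the drift, which the documents do not give.

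**The case against.** The strongest reply is that the surviving conflict is narrow and that much of the information is reported anyway.

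- **The Week 40 baseline is not itself an error.** It suits a Part 2 period analysis, and it does not enter the TEAE rule in SAP 9.1, which works from event dates and worsening. This stands: the baseline rule bears on laboratory, vital-sign and weight change, not on the Part 2 primary endpoint.
- **The protocol promises less than a full combined safety package.** Protocol 9.8 covers events and 9.3 covers exposure. Combined laboratory or vital-sign change and exposure-adjusted rates are not promised. This stands, and those items are offered below as additions.
- **Existing outputs mitigate.** SAP 9.3 summarises observed vital signs, including weight, at each visit, and SAP 9.2 summarises laboratory data by visit. Worst laboratory category against the reference range and worst investigator vital-sign assessment do not depend on a Week 40 change. Adverse event listings give onset relative to first dose. This stands in part. A reader could set Week 76 means beside Part 1 baseline means, but the populations differ through attrition, and none of these outputs is a cumulative incidence or a within-subject cumulative change.
- **Absence cannot be fully verified.** SAP 4.1.2 and 12.2 allow exceptions, the change-from-baseline formulas are not visible, and the table shells are not supplied. This limits the claim to the visible text.

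A reader might also infer three stronger claims that the documents do not support. One is that the two parts are never combined anywhere, which Protocol 9.8 and 9.3 contradict. Another is that every Part 2 change is measured from an on-drug value, which is untrue of former placebo subjects. The third is that Part 2 tables understate true change by a known 53%. The 47% and 53% are shares of time, not estimates of bias.

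**Conclusion.** The point holds in a limited form. The SAP's by-part rule conflicts with the protocol's plan for combined treatment-emergent events and pooled exposure. Followed as written, it gives no cumulative incidence or change since first K0706 dose for the early-start arms. Those arms are about two thirds of randomized subjects, roughly 337 of 506 before attrition, or 202 to 337 in Part 2 if 60% to 100% roll over. Their Part 2 changes cover 36 of up to 76 weeks on drug.

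The gap matters because long-term safety is the Part 2 primary objective and TEAE incidence its primary endpoint. No data are lost, the Part 1 efficacy inference is untouched, and QTcF is unaffected. The conclusion assumes that the redacted text and unseen table shells contain no combined safety output. It does not establish that the Part 2 'overall' column is biased, only that it mixes two kinds of baseline.

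**What to change.** Reconcile Protocol 9.8 and 9.3 with SAP 9.0 and 9.8 by adding a combined K0706-exposure summary to the SAP, by treatment group (early-start low dose, early-start high dose, former placebo):

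1. **TEAE incidence and exposure counted from the first K0706 dose**, in all safety-set subjects who received K0706, including those who never entered Part 2. Add exposure-adjusted rates, because follow-up on drug runs to 76 weeks in early-start subjects and 36 weeks in former placebo subjects.
2. **Laboratory, vital-sign and weight change from the last value before the first K0706 dose**: the Part 1 baseline for early-start subjects and the Week 40 value for former placebo subjects.
3. **Existing tables kept.** Retain the Part 1 and Part 2 tables, and footnote the Part 2 'overall' change column to say that it mixes on-drug and pre-drug baselines.

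The combined events and pooled exposure restore what the protocol already plans. The exposure-adjusted rates and the combined change tables are additions. The cost is one extra set of tables from data already collected, with no change to visits, sample size or the Part 1 analysis.

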4.1.3 Treatment Period

If the time (HH:MM) of data collection is not recorded but the protocol and / or eCRF includes an instruction to the effect that all Day 1 assessments are to be performed prior to the first dose of study drug administration, the data collected at Day 1 will be assigned to the Baseline period. However, adverse events (AEs) and medications starting on Day 1 with missing onset time (HH:MM), will be assigned to the Treatment Period.

The Treatment Period is defined as the period from the date/time of the first dose of study drug administration up to and including the date of the last dose of study drug administration.

4.1.4 Visit Windows

[figure not shown]
4.1.4.1 Part 1

Table 3 provides the relative study day ranges to be applied to the assessment/sample collection dates to derive the analysis Visits for efficacy analyses and some safety assessments (vital signs, laboratory assessments, and C-SSRS, by Visits for Part 1).

The following considerations are to be followed when deriving the analysis Visits:

- Both scheduled and unscheduled assessments are included for visit windowing

 If both scheduled and unscheduled assessments fall within the same visit window, the scheduled assessment with non-missing assessment results will be used for analysis

Statistical Analysis Plan	CONFIDENTIAL	
		Protocol Reference: CLR_18_06
4.1.4.2 Part 2		
Table 4 provides the relative study day dates to derive the analysis Visits for a laboratory assessments.		
The above considerations for Part 1 are Part 2.	e also to be followed when d	eriving the analysis Visits for
4.2 Handling of Dropouts, Missing D	ata, and Outliers	
LACE WILL CAR TO DOOR TO	65.5 80. 1	

4.2.1 Handling of Missing Efficacy Data

In general, missing efficacy	data will not be imputed for efficacy analyses. The analyses
will be based on	The only exception is that a set of supplementary
	of the primary efficacy variables at Week 40 will be
performed on	imputed data.

4.2.2 Handling of Missing Safety Data

In general, missing clinical laboratory data, vital signs, and ECG data will not be imputed. Adverse event imputations for missing severity or relationship are described in Section 9.1. Unknown or partial medication and AE date imputations are given below and are to be used only for the assessment of prior/concomitant status for medications and treatment-emergent status for AEs.

4.2.3 Handling of Partial and Missing Dates for Adverse Events, Prior / Concomitant Medications, and Last Dose of Study Drug

For AEs with partial or missing onset or stop dates:

- AE stop date will be imputed first as:
 - o If the stop date is completely missing, assume it is ongoing (no imputation);
 - o For a partial AE stop date:
 - the day is missing, then take the last day of the month
 - both day and month are missing, then take December 31st.
 - o If the imputed AE stop date is after the End of the Study date, then the stop date will be set to the End of the Study date.
- Then AE onset date will be imputed as:
 - o If the onset date is completely missing, the first dose date;
 - o For a partial AE onset date:
 - Day is missing:
 - Partial date < the first dose date: last day of the month
 - Partial date = the first dose date: the first dose date
 - Partial date > the first dose date: first day of the month
 - Both day and month are missing, ie, only the year is available:
 - Partial date < the first dose date: 31st December
 - Partial date = the first dose date: the first dose date
 - Partial date > the first dose date: 1st January.
 - o If the imputed AE onset date is after the AE stop date/imputed AE stop date, then the onset date will be set to the AE stop date/imputed AE stop date.

In the event that a partial date (month/year or year) for concomitant medication is available, concomitant medication start and stop dates will be imputed as:

• When both month and year are available – the first day of the month will be used for the start date, and the last day of the month will be used for the stop date.

Protocol Reference: CLR 18 06

• When only year is available – 01 January will be used for the start date and 31 December will be used for the stop date.

Study drug last dose date (based on "Last Study Drug Details" eCRF page) will be used for calculating the exposure to study drug. If the study drug last dose date is missing, alternatively the date of the last dose from the "DOSING" eCRF page will be used for the imputation. This imputation of the study drug last dose date will be applied to both Part 1 and Part 2 of the study.

The imputed dates will not be listed. Study day relative to the first dose of the study drug and duration associated with missing or partial dates will not be displayed in AE and concomitant medication listings.

4.2.4 Handling of Plasma and CSF Concentrations that are Below the Lower Limit of Quantification

Plasma and CSF concentrations that are below the lower limit of quantification (BLQ) will be handled as follows for descriptive statistics:

- Values that are BLQ will be set to 0 for the calculation of summary statistics.
- Arithmetic mean or median values that are BLQ will be presented as 0.
- If any BLQ results (treated as 0) are in a series of summarized data, the geometric mean and coefficient of variation (CV)% of the geometric mean will be reported as not calculated (NC).

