- Pharmacokinetics Plasma and CSF levels of K0706 and any relevant metabolites.

Safety / Tolerability Endpoints:

- Vital Signs
- Electrocardiography (ECG)
- Laboratory values
- Adverse Events (AEs)
- •

Exploratory Endpoints:

- Skin pathological findings that correlate with PD,
- Blood and CSF levels of emerging biomarkers (progression or target engagement of K0706.
- Brain DaT SPECT an imaging tool that is a marker of dopaminergic cell health.
- •

Part 2 (Weeks 40 to 80)

Protocol CLR 18 06, EudraCT 2018-003337-15 A06 – 23 October 2023 K0706 Name of Sponsor: Sun Pharma Advanced Research Company Limited (SPARC) Name of Investigational Product: K0706 / placebo **Primary endpoint:** • Incidence of treatment-emergent adverse events **Secondary endpoints:** • Change from Week 40 (Baseline for Part 2) to Week 76 of the long-term extension study in the MDS-UPDRS Part III score • Change from Week 40 (Baseline for Part 2) to Week 76 of the long-term extension study in MDS-UPDRS Parts II and III sum score • Change from Week 40 (Baseline for part 2) through Week 76 in MDS-UPDRS Part IA, Part IB, Part I total, Part II total, and Part III sub-scores Change in MDS-UPDRS grand total score (sum of Parts I, II, and III) from Week 40 (Baseline for part 2) through Week 76 Time from Week 40 (Baseline for Part 2) to initiation of symptomatic PD medications in the longterm extension study **Exploratory endpoints:** Change in the mean MDS- UPDRS Parts I, II and III scores between the early-start and delayedstart groups at 76 weeks

- Evaluation of slopes of the mean MDS-UPDRS Parts II and III scores over time in part 2 for the early-start group as compared to the delayed-start group
- The proportion of patients starting symptomatic PD treatment

Study Design
This is a randomized, double-blind, placebo-controlled, to evaluate the efficacy, safety and tolerability of two doses of K0706 compared to placebo in subjects with early PD. This study consists of two parts. Part 1 is designed to evaluate the
efficacy, safety, and tolerability of two dose levels of K0706 compared to placebo in subjects with early
PD who are not receiving dopaminergic therapy. Part 2 is an optional long-term extension study to assess the long-term safety/tolerability of K0706 in subjects with early PD.
Part 1:

Name of Sponsor: Sun Pharma Advanced Research Company Limited (SPARC)
Name of Investigational Product: K0706 / placebo

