9.1 Adverse Events

All AEs recorded on the eCRF will be coded using the MedDRA dictionary (version 23.0 or a later version if updated during the study) and classified as either pre-treatment AEs or TEAEs for Part 1 or Part 2 of the study as follows:

- Pre-treatment AEs are events that start prior to the start of the Treatment Period.
- TEAEs are either events with start date / time on or after the start of the Treatment Period, or events with start date / time prior to the start of the Treatment Period whose severity worsens on or after the start of the Treatment Period.
- TEAEs for Part 1 of the study are all TEAEs for those subjects not participating in Part 2 of the study and those TEAEs with start date / time before the date of first dose for Part 2 of the study for subjects participating in Part 2 of the study.
- TEAEs for Part 2 of the study are those TEAEs with start date / time on or after the date of first dose for Part 2 of the study.
- Serious TEAEs will be defined as TEAEs regarded by the investigator as Serious = "Yes".
- The relationship between TEAE and study medication is assessed as certainly, probably, possibly, unlikely or unrelated. A study treatment related TEAE will be defined as a TEAE considered by the investigator as certainly, probably, or possibly related to study medication or with missing relationship to study medication.
- Assessment of AE severity will be characterized as mild, moderate, severe, life-threatening and death.
- TEAEs leading to discontinuation of study are defined as TEAEs where "Did AE caused subject to discontinue from the study?" is indicated as "Yes".
- TEAEs leading to discontinuation of study treatment are defined as TEAEs where "Action taken with Study Medication" is indicated as "Drug Discontinued".

AEs will be summarized by default descriptive summary statistics for categorical variables by treatment group and overall, for Parts 1 and 2 of the study separately, using the Safety Analysis Set, Part 1 and Safety Analysis Set, Part 2 respectively, as follows:

• An overview of TEAEs including the number and percentage of subjects with at least one of each mentioned TEAE type:

- Any TEAE
 - Leading to discontinuation of study treatment
 - Leading to death
 - Severity: mild
 - Severity: moderate
 - Severity: severe
 - Severity: life-threatening
 - Severity: death
- Any study treatment-related TEAE
 - Leading to discontinuation of study treatment
 - Leading to death
- Any serious TEAE

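### The adverse-event date-imputation rule ignores the Part 2 first dose, so onsets with incomplete dates that could straddle the placebo-to-K0706 switch default to Part 1

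*SAP*

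**What the plan says.** SAP 4.2.3 compares a partial onset with the first dose date, without naming a Part. If the day is missing and the month is that of the first dose, onset becomes the first dose date. If the month is later, the rule is "Partial date > the first dose date: first day of the month". Year-only dates are handled in the same way: same year, the first dose date; later year, "Partial date > the first dose date: 1st January". For no date at all: "If the onset date is completely missing, the first dose date". The one further adjustment can only move an onset earlier: "If the imputed AE onset date is after the AE stop date/imputed AE stop date, then the onset date will be set to" the stop date.

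SAP 4.2.2 says that imputed dates "are to be used only for the assessment of prior/concomitant status for medications and treatment-emergent status for AEs". SAP 9.1 then defines Part 2 events as "those TEAEs with start date / time on or after the date of first dose for Part 2 of the study"; for Part 2 participants, anything earlier is a Part 1 event.

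Part 2 is where the placebo group first takes K0706, at the high dose. SAP 2.1.2 gives the purpose: "This will enable the collection of additional safety data for the high dose level". The Part 2 primary endpoint in the protocol synopsis is "Incidence of treatment-emergent adverse events".

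**The concern.** The same-month and same-year conventions protect the first exposure to study drug: an onset that could fall on either side of the first dose is counted as treatment-emergent. For a subject randomised to placebo, the first exposure to K0706 is the Part 2 first dose, and no matching convention exists there. An incomplete date around the switch is pulled back before it, and SAP 9.1 then counts the event in Part 1, under placebo.

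At stake is the Part 2 primary endpoint in the group whose crossover is meant to supply high-dose safety data. The tabulation of events by actual dose at onset (Protocol 9.8.1) could be affected too. The misplacement would be hard to spot, because SAP 4.2.3 does not list imputed dates.

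**Working it through.** **Which first dose is meant.** SAP 4.1.1 relates all assessment days to the first dose, taken from the Baseline Visit forms, and defines the Part 2 first dose separately from its own form. Where the SAP wants both Parts covered, it says so: the last-dose imputation in 4.2.3 is applied to both Parts, and the medication listings in 9.7 count days from the first dose of the corresponding Part. The onset rules have no such wording. The Part 1 dose is therefore the natural reading, but it is inferred.

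**Setup.** The documents give no figure to reproduce, so I enumerated the rules. From the documents: Part 2 treatment lasts 36 weeks (36 × 7 = 252 days), or 40 weeks to the Week 80 visit (40 × 7 = 280 days). Assumed: Part 1 first dose on each of 1,461 consecutive dates (four calendar years); Part 2 first dose exactly 280 days later; true onset uniform over Part 2; stop date missing or not binding. An event is misplaced if its imputed onset is before the Part 2 first dose.

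**Results**, as misplaced ÷ all post-switch onset days:

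| Onset information | 252 days (1,461 × 252 = 368,172) | 280 days (1,461 × 280 = 409,080) |
|---|---|---|
| Day missing | 21,520 ÷ 368,172 = 5.8% | 21,520 ÷ 409,080 = 5.3% |
| Year only | 240,660 ÷ 368,172 = 65.4% | 251,720 ÷ 409,080 = 61.5% |
| Wholly missing | 100% | 100% |

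Over 252 days, the share for a single start date runs from 0% to 11.9% (day missing) and from 0% to 100% (year only).

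**Where the errors fall (252 days).**
- Day missing: all 21,520 are in the calendar month of the switch, out of 22,981 onset days in that month. The other 1,461 belong to switches on the 1st, where the rule works. In later months, 0 of 345,191 are misplaced.
- Year only: all 240,660 are in the calendar year of the switch, out of 241,668. The other 1,008 (4 × 252) belong to switches on 1 January. In the following year, 0 of 126,504 are misplaced.

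**Example.** Part 1 first dose 10 January 2022; Part 2 first dose 17 October 2022.

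| True onset | Known | Imputed | Part assigned |
|---|---|---|---|
| 25 Oct 2022 | month and year | 1 Oct 2022 | 1 (wrong) |
| 20 Nov 2022 | month and year | 1 Nov 2022 | 2 (right) |
| 5 Dec 2022 | year | 10 Jan 2022 | 1 (wrong) |
| 5 Mar 2023 | year | 1 Jan 2023 | 2 (right) |
| 5 Mar 2023 | nothing | 10 Jan 2022 | 1 (wrong) |

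**Would swapping the reference date cure it?** No. With the Part 2 first dose as the only reference, no post-switch event goes to Part 1, but true Part 1 events go to Part 2: 5.3% of day-missing, 61.5% of year-only and 100% of wholly missing onsets.

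**The case against.** **The scope sentence in SAP 4.2.2.** It limits imputed dates to treatment-emergent status and does not mention allocation to a Part. Read strictly, the SAP then has no rule for the split rather than a wrong one. But SAP 9.1 defines treatment-emergent events for Part 1 and for Part 2, so the limit most naturally covers that split. The SAP needs a clarifying sentence on either reading.

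**A Part-specific reading of first dose.** SAP 9.1 reports each Part separately, so one could use each Part's own dose. The same event could then be dated before the switch for Part 1 and on it for Part 2, with no tie-break.

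**Few dates will be affected.** Start date is a required item and subjects are asked about the time since the last questioning (Protocol 8.4); discrepancies are queried before lock (Protocol 10.4). Year-only and wholly missing onsets, which carry the large percentages, should be the rarest. Tables also count subjects, so one moved event need not change overall incidence, and Protocol 9.8 describes events for both Parts combined, where the event is kept. This stands and limits the importance of the point.

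**Stronger inferences the documents do not support.**
- A reader might infer that every post-switch event with a partial date goes to placebo. Later months and later years are placed correctly, and only subjects randomised to placebo are charged to placebo. In the K0706 arms the event changes Part but stays with the same randomised group.
- A reader might infer that the Part 1 difference between K0706 and placebo must narrow. The same rule adds Part 2 events to the K0706 arms' Part 1 columns, and nothing shows that placebo gains more.
- Early clustering of onsets would raise the shares, for example to about 27% (day missing) and 88% (year only) with an exponential onset of mean 45 days capped at 280. The documents give no basis for that distribution.

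**Conclusion.** The gap is real but narrow. On the natural reading of SAP 4.2.3 and 9.1, a post-switch event defaults to Part 1 when its known date fits both sides of the Part 2 first dose: day missing in the switch month (unless the switch was on the 1st), year only in the switch year (unless it was on 1 January), or no onset date. For prior-placebo subjects, an event on K0706 then leaves the Part 2 primary endpoint and enters the Part 1 placebo column.

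The shares of 5–6%, 61–65% and 100% are shares of the post-switch onsets with that kind of missing date. They rest on uniform onset, a switch exactly 280 days after the first dose and a non-binding stop date. The number of partial dates is unknown and the absolute count probably small. The Part 1 reference date is inferred, and the net effect on the Part 1 comparison is not established. Because a primary endpoint is involved and the remedy is cheap, the SAP should be corrected.

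**What to change.** In SAP 4.2.3 and 9.1, state which first dose is meant and that imputed dates drive the Part split. Then add a rule for prior-placebo subjects treated in Part 2. Impute onset as the Part 2 first dose date when all three conditions hold:

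1. the known part of the onset date fits both Parts;
2. the actual or imputed stop date is not before the Part 2 first dose;
3. the event was not already recorded at a visit before that dose.

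Otherwise, and for subjects continuing on K0706, keep the existing rule. For year-only or wholly missing onsets, let the visit at which the event was first recorded decide the Part. The stop date alone often will not: a missing one is taken as ongoing, and a partial one goes to month-end or 31 December.

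The rule should not send every ambiguous onset in all arms to Part 2. That would remove true Part 1 K0706 events from the only placebo-controlled safety table, which is not conservative, and for year-only or wholly missing dates it would largely reverse the error.

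Cost: a few lines of SAP text and code. Downside: a few true placebo-period events will be attributed to K0706, which is the conservative direction.
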